9.2 Statistical Analysis of Reference Variables

For the AUC_{∞} , MRT_{∞} , t_{max} , and λ_z of tolvaptan, data (excluding t_{max}) will be log-transformed and analysis of variance (ANOVA) will be performed using group (group receiving conventional tablet first, group receiving OD tablet without water first, and group receiving tolvaptan OD tablet with water first), formulation and dosing regimen, subjects within group, and administration period (Period 1, Period 2, and Period 3) as factors. The analysis will use natural logarithms. The effects of the formulation and dosing regimen will be analyzed at a significance level of 5%.

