1	15	Tolvaptan 15 mg	1 tablet	With water: Administered with approx. 150 mL of water.
2	30	Tolvaptan 30 mg		Without water: Tablet disintegrated on the tongue and swallowed immediately with saliva
[Comparator: Tolvaptan conventional tablet]				
Cohort	Dose (mg)	Active Ingredient (Content per tablet)	Dose per Administration	Dosing Regimen (Single oral administration in a fasting state)
1	15	Tolvaptan 15 mg	1 tablet	Administered with approx. 150 mL of water.
2	30	Tolvaptan 30 mg		
Duration of treatment: Single administration a total of 3 times on 3 separate days				

Protocol 156-102-00136

Variables:	
[Bioequivalence]
 
 1) Primary variables: AUC_t and C_{max} of tolvaptan 2) Reference variables: 
 • Plasma concentration-time profile of tolvaptan • AUC_{∞}, MRT_{∞}, t_{max}, λ_z, $AUC\%Extrap$, $t_{1/2,z}$, CL/F, $CL/F/BW$, and t_{last} of tolvaptan • By-subject ratios of AUC_t, C_{max}, AUC_{∞}, MRT_{∞}, and λ_z of tolvaptan for administration of OD tablet with and without water to those for administration of conventional tablet • Difference (value for OD tablet minus value for conventional tablet) in t_{max} by subject between administration of OD tablet without water and administration of conventional tablet and between administration of OD tablet with water and administration of conventional tablet 
[Safety Variables]
 
Body weight, vital signs (body temperature, blood pressure, and pulse rate), clinical laboratory tests, 12-lead electrocardiography (ECG), physical examination, and adverse events

Statistical Methods:	
For the AUC_t and C_{max} of tolvaptan, data will be log-transformed and analysis of variance (ANOVA) will be performed using group (group receiving conventional tablet first, group receiving OD tablet without water first, and group receiving tolvaptan OD tablet with water first), formulation, dosing regimen, subjects within group, and administration period (Period 1, Period 2, and Period 3) as factors.
 
For the AUC_t and C_{max} of tolvaptan, the 90% confidence interval (CI) of the ratio of the geometric mean values for the 2 formulations (OD tablet without water vs conventional tablet and value for OD tablet with water vs conventional tablet) will be calculated.
 
If evaluable data cannot be obtained for a subject for all periods (1, 2, and 3), sensitivity analysis will be performed including such subjects.

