7.1 Sample Size

With reference to the Guidelines for Bioequivalence Studies of Generic Products,¹ the sample size for this study was calculated as the number of subjects required to demonstrate that the 90% confidence intervals of the geometric mean ratios of the AUC_t and C_{\max} of tolvaptan (OD tablet without water vs conventional tablet and OD tablet with water vs conventional tablet) fall inside the bioequivalence range of $\ln(0.8)$ to $\ln(1.25)$.

Of the prior crossover studies of tolvaptan in healthy adults, Study 156-00-002 reported the largest intra-individual variability (AUC_t and C_{\max} , 0.033 and 0.056, respectively). Sample size calculation was performed using the method proposed by Diletti, et al. (1991)⁵ based on the C_{\max} , in which intra-individual variability was large.

When the ratio of the expected C_{\max} with the tolvaptan OD tablet (administered with or without water) to that with the tolvaptan conventional tablet is assumed to be 1.05, at least 12 subjects per group are required to achieve a power of at least 90%. To account for withdrawals and dropouts, the sample size for this study was set to 14 subjects per group for 1 cohort, for a total of 42 subjects.

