- 2) For the AUC_t and C_{max} of tolvaptan, the 90% confidence intervals of the ratio of the geometric mean values for the 2 formulations (OD tablet without water vs conventional tablet and OD tablet with water vs conventional tablet) will be calculated. Bioequivalence between the formulations and between the dosing regimens is to be demonstrated when the 90% confidence intervals fall inside the range of $\ln(0.8)$ to $\ln(1.25)$. Bioequivalence between the OD tablet and conventional tablet is to be established when the bioequivalence criteria are met between the OD tablet administered without water and conventional tablet and also between the OD tablet administered with water and conventional tablet. When an add-on subject study is conducted, bioequivalence is to be assessed in the same manner with the pooled data of both the main study and add-on subject study, using the study as a variation factor.

- 3) When there are discontinued subjects or unevaluable data, a sensitivity analysis will be performed. Log-transformed AUC_t and C_{max} values will be analyzed with a linear mixed-effects model, using group, administration period, and formulation and dosing regimen as fixed effects and subjects within group as a random effect, and the difference between formulations (OD tablet without water – conventional tablet and OD tablet with water – conventional tablet) and corresponding 90% confidence intervals will be calculated.

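### AUC∞, MRT∞, λz and tmax get only a 5% difference test; add model-based contrasts with 90% CIs against the conventional tablet

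*SAP*

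**What the plan says.** SAP 9.2 and Protocol 7.4.2 use the same wording. AUC∞, MRT∞ and λz (on the log scale) and tmax (untransformed) go into an ANOVA whose terms are sequence group and "formulation and dosing regimen, subjects within group, and administration period (Period 1, Period 2, and Period 3) as factors". The inference is then: "The effects of the formulation and dosing regimen will be analyzed at a significance level of 5" per cent. Neither section names the test statistic, a pairwise contrast or an interval.

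The primary variables are handled differently. In SAP 9.1, bioequivalence for AUCt and Cmax "is to be demonstrated when the 90% confidence intervals fall inside the range of" ln(0.8) to ln(1.25). The comparisons are "OD tablet without water vs conventional tablet and OD tablet with water vs conventional tablet", and both must pass.

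Some descriptive output against the conventional tablet is planned. SAP 6.2 items 3 and 4 and SAP 9.3.2 define by-subject ratios (AUC∞, MRT∞ and λz among them) and by-subject tmax differences for each OD regimen. SAP 9.4.2 gives their reporting precision, but its list of descriptive statistics refers to SAP 6.1 and SAP 6.2 items 1 and 2, not to items 3 and 4.

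**The concern.** AUC∞ and AUCt describe nearly the same exposure. The plan asks of AUCt whether the difference is small, and of AUC∞ whether there is any difference at all. A significant result is compatible with a ratio well inside 0.80 to 1.25, and a non-significant result does not show similarity. Neither answers the trial's question.

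Read as a single three-level factor, the treatment term has 2 degrees of freedom. It then takes in OD with water versus OD without water, which is no part of the decision rule, and a significant result does not say which OD regimen departs from the conventional tablet.

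At stake is what the report can say about the reference variables, and how a reader is to take a significant AUC∞ effect printed next to a bioequivalent AUCt. The plan gives no rule for reading that pair.

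**Working it through.** **Inputs.** 42 subjects per cohort, true ratio 1.05 for Cmax and power of at least 90% (Protocol 7.1, SAP 4). For variability, the prior study chosen "reported the largest intra-individual variability (AUC_t and C_{\max} , 0.033 and 0.056, respectively"), read here as log-scale variances. Residual degrees of freedom for the three-period crossover: 2N − 4 = 80 at N = 42.

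**Assumptions not in the documents.** AUC∞ has the AUCt variance, 0.033; the true ratios are the same for AUCt and AUC∞; their within-subject correlation is 0.99 (0.90 gives nearly the same results). The 1.05 is borrowed from Cmax, and the other ratios are illustrative.

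**The plan's own figure.** Power of the two one-sided tests for Cmax (variance 0.056, ratio 1.05) first reaches 90% at N = 34 with N − 2 df (0.9065) or N = 33 with 2N − 4 df (0.904). Three equal groups of 12 (N = 36) give 0.921 to 0.926. The stated 12 per group is reproduced.

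**Where the two criteria overlap (N = 42, variance 0.033).**
- SE of a contrast = √(2 × 0.033/42) = 0.0396.
- 90% CI half-width = 0.066, so AUCt passes up to an observed ratio of exp(0.223 − 0.066) ≈ 1.17.
- The 5% critical value of F with 2 and 80 df is 3.111. If both OD arms shift by D, F = N·D²/(3s²). It is significant from D = √(3 × 3.111 × 0.033/42) = 0.0856, a ratio of about 1.089.
- With the third arm midway between two extremes, D = √(4 × 3.111 × 0.033/42) = 0.0989, a ratio of about 1.104.

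If both OD arms show the same observed ratio, anywhere from about 1.09 to 1.17 satisfies both criteria.

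**How often (200,000 simulated cohorts per row, N = 42).** AUCt must pass for both OD regimens; the F-test is on AUC∞.

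| True ratio with / without water | AUCt bioequivalent | AUC∞ test significant | Both | Of those, water contrast largest |
|---|---|---|---|---|
| 1.00 / 1.00 | 100% | 5.0% | 5.0% | about 1/3 |
| 1.05 / 1.05 | 99.4% | 22.1% | 21.5% | 5% |
| 1.10 / 1.10 | 89.6% | 68.2% | 57.8% | 0.4% |
| 1.00 / 1.05 | 99.7% | 22.2% | 21.9% | 48% |
| 1.05 / 1.10 | 93.7% | 55.3% | 48.9% | 8.5% |
| 0.95 / 1.05 | 99.3% | 59.4% | 58.7% | 86% |

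In at least 94% of the cohorts in the Both column, the AUC∞ 90% CIs for both contrasts would also lie inside 0.80 to 1.25.

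**Sensitivity.** At N = 36, the 1.05/1.05 figure is 17.8%. If the AUC∞ variance were 0.02, the significance threshold falls to exp(√(3 × 3.111 × 0.02/42)) ≈ 1.069, and the test is significant in about 34% of cohorts at 1.05/1.05. At 0.056 the threshold rises to about 1.118. Nothing was computed for MRT∞, λz or tmax, because the documents give no variance for them.

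**The case against.** The strongest reply is that nothing rides on these tests. Only AUCt and Cmax decide bioequivalence, and no section makes a significant reference-variable effect a failure or a trigger for the add-on study. A detectable difference inside 0.80 to 1.25 is logically compatible with bioequivalence. This stands. A reader might infer that the trial could return opposite verdicts; the documents do not support that.

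A reader might also infer that the water comparison will often be what makes the test significant. On the plan's assumption of one ratio for both OD regimens it is the largest contrast in about 5% of the coinciding results. It dominates only if the regimens fall on opposite sides of the conventional tablet, which nothing in the documents suggests. What holds is that the test can be driven by that contrast.

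Nor is it right that no comparison with the conventional tablet is planned: by-subject ratios and tmax differences are, and geometric means by regimen for all parameters except tmax and tlast would show direction and size. What these sections lack is a model-based ratio with an interval. The contents of SAP Appendix 1 (list of tables) were not in the text available, so a table specified only there could not be checked.

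Finally, the three-arm test is an inference from the combined factor. The synopsis lists "formulation, dosing regimen, subjects within group, and administration period" for the primary ANOVA, which can be read as two terms. The conventional tablet is given only with water, so a separate regimen term, adjusted for formulation, would test OD with versus without water directly. The wording needs settling on either reading.

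The protocol says it broadly follows a bioequivalence guideline, and the 5% test may be there by convention. That is a reason to allow it to stay, not a reason to leave out the intervals.

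**Conclusion.** The point holds as a minor one about analysis and reporting. The only inference planned in SAP 9.2 and Protocol 7.4.2 for four reference variables is a difference test, which does not measure similarity and, read as a three-level factor, does not identify the regimen concerned. On the stated assumptions, a cohort would show AUCt bioequivalent with a significant AUC∞ effect in about 21.5% of cases at true ratios of 1.05 and about 58% at 1.10. These sizes depend on an AUC∞ variance the documents do not give and on ratios assumed for illustration or borrowed from Cmax. The bioequivalence conclusion itself is not affected.

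**What to change.** In SAP 9.2 and Protocol 7.4.2:

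- From the same ANOVA, estimate OD without water versus conventional and OD with water versus conventional. Report geometric mean ratios with 90% CIs for AUC∞, MRT∞ and λz.
- For tmax, report the same two differences with 90% CIs, and note that sampling is hourly up to 6 hours, so the values are coarse and the interval approximate. SAP 9.4.2 summarises tmax only by number, minimum, median and maximum, so the estimated difference adds information.
- State whether formulation and dosing regimen form one factor or two, and align the synopsis.
- If the 5% test is kept, name it, label it descriptive, and say that it is not the basis for judging similarity and does not alter the bioequivalence conclusion.

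The cost is a few sentences and some extra table columns, with the same model and data. The plan sets no equivalence range for these variables, and none is needed to report the intervals.

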9.3 Methods of Pharmacokinetic Analysis

9.3.1 Blood Collection Time Points

In each period, before IMP administration and 1, 2, 3, 4, 5, 6, 8, 10, 12, and 16 hours postdose

9.3.2 Method of Calculating Pharmacokinetic Parameters

- 1) AUC_t , C_{max} , AUC_{∞} , MRT_{∞} , t_{max} , λ_z , $AUC\%$ Extrap, $t_{1/2, z}$, t_{last} , CL/F , λ_z (point), λ_z (lower), λ_z (upper) and λ_z (Rsq) are to be calculated per subject by non-compartmental analysis.
- 2) $CL/F/BW$ is to be calculated by dividing CL/F by the body weight (kg) before IMP administration in each period.
- 3) The ratio between the formulations and regimens is to be calculated per parameter in each subject by $[Value\ after\ dosing\ of\ OD\ tablet\ without\ water] / [Value\ after\ dosing\ of\ conventional\ tablet]$ and $[Value\ after\ dosing\ of\ OD\ tablet\ with\ water] / [Value\ after\ dosing\ of\ conventional\ tablet]$ (parameters, AUC_t , C_{max} , AUC_{∞} , MRT_{∞} , and λ_z).
- 4) Differences in t_{max} ($[t_{max}\ after\ dosing\ of\ OD\ tablet\ without\ water] - [t_{max}\ after\ dosing\ of\ conventional\ tablet]$) and also ($[t_{max}\ after\ dosing\ of\ OD\ tablet\ with\ water] - [t_{max}\ after\ dosing\ of\ conventional\ tablet]$) are to be calculated per subject.

9.4 Technical Details of Pharmacokinetic Statistical Analysis

9.4.1 Exclusion From Pharmacokinetic Analysis

9.4.1.1 Blood Collection Time Points Outside the Acceptable Time Windows

If blood is collected at a time point outside the acceptable time window, and it is determined that the data is unsuitable for calculation of descriptive statistics for plasma concentrations, the data will be excluded from the calculation of descriptive statistics for plasma concentrations while it will be included in pharmacokinetic analysis.

9.4.1.2 In the Event Vomiting Occurs

With reference to the Food and Drug Administration (FDA) guidance,³ if vomiting occurs at a time point less than twice the median t_{max} , the data for this period for the subject who experienced vomiting will be excluded from pharmacokinetic analysis. The median t_{max} that is referenced for that judgment is the median of the same group in the same study calculated excluding the vomiting case.

9.4.1.3 In the Event Prohibited Medications Are Used

If prohibited medications that may affect the pharmacokinetics of IMP are used, data points after the use of prohibited medications in the relevant subjects will be excluded from pharmacokinetic analysis.

9.4.2 Reporting of Concentrations and Parameters

- 1) Values below the lower limit of quantitation occurring at time points before the first quantified level for drug concentration will be treated as 0.
- 2) Values below the lower limit of quantitation occurring at time points after the first quantified level for drug concentration will be treated as missing.
- 3) Descriptive statistics for parameters listed in [Section 6.2](#) 1) will be calculated at each blood collection point, for each cohort, for administration of the conventional tablet, OD tablet without water, and OD tablet with water. Descriptive statistics for parameters listed in [Sections 6.1](#) and [6.2](#) 2) will be calculated for each parameter, for each cohort, for administration of the conventional tablet, OD tablet without water, and OD tablet with water. The descriptive statistics calculated for plasma drug concentration will be number of subjects, arithmetic mean, standard deviation, coefficient of variation, minimum, median, and maximum, the descriptive statistics calculated for parameters other than t_{max} and t_{last} will be number of subjects, arithmetic mean, standard deviation, coefficient of variation, geometric mean, minimum, median, and maximum, and the descriptive statistics calculated for t_{max} and t_{last} will be number of subjects,

minimum, median, and maximum. Descriptive statistics will not be calculated for λ_z (Rsq), λ_z (point), λ_z (upper), or λ_z (lower).

- 4) Arithmetic means and standard deviations will be used to plot plasma concentration-time profile.
- 5) Individual values and descriptive statistics for pharmacokinetic parameters are displayed using the number of digits presented in [Table 9.4.2-1](#). Coefficient of variation (CV%), which is used as a descriptive statistic, will be rounded off to 1 decimal place.

Table 9.4.2-1 Handling of Numerical Values	
AUC _t , AUC _∞	3 significant figures
AUC% Extrap	1 decimal place
C _{max}	3 significant figures
CL/F, CL/F/BW	3 significant figures
MRT _∞	1 decimal place
t _{max}	1 decimal place
t _{last}	1 decimal place
t _{1/2,z}	1 decimal place
λ_z	3 significant figures
λ_z (point)	Whole numbers
λ_z (lower), λ_z (upper)	2 decimal places
λ_z (Rsq)	4 decimal places
Geometric mean ratio (GMR)	4 decimal places
Confidence interval of GMR	4 decimal places
By-subject ratio	2 decimal places
Difference in t _{max} by subject	1 decimal place

10 Pharmacodynamic Analysis

